7.7. Criteria for Study Termination

The Sponsor reserves the right to terminate the study at any time. In addition, the Sponsor may terminate the study at an investigational site at any time (e.g., Good Clinical Practice [GCP] noncompliance or poorly performing sites, as determined by the number of subjects enrolled or the quality of the study data).

The Investigator and/or Sponsor (or designee) must notify the Institutional Review Board/Independent Ethics Committee (IRB/IEC) of discontinuation of a site or the study and the reason for doing so.

Investigators will be informed by the Sponsor as to when the final study visit is to be completed and should then schedule all subjects for the EOS Visit.

8. SELECTION AND WITHDRAWAL OF SUBJECTS

8.1. Subject Population

This study will be conducted at approximately 60 investigational study sites, globally, with experience in treating subjects with PBC. Subjects will be transitioning from Study 747-213 and Study 747-124 (or other Sponsor studies) if they continue to meet the following criteria.

8.2. Subject Inclusion Criteria

1. All subjects with PBC who participated and are actively taking investigational product in Study 747-213 or Study 747-214 (or other Sponsor studies) are eligible to enroll in this study (977-311).

- Subjects on a drug holiday within the previous 60 days due to unresolved TEAEs or SAEs in the parent study should discuss eligibility for rolling over to this study with the Sponsor Medical Monitor.
2. Contraception: Female subjects must be postmenopausal, surgically sterile, or, if premenopausal (and not surgically sterile), be prepared to use ≥ 1 highly effective method of contraception during the study and for at least 30 days after the last dose of investigational product. Highly effective methods of contraception per the Clinical Trials Facilitation and Coordination Group guidelines are those that alone or in combination results in a failure rate of less than 1% per year when used consistently and correctly. These highly effective contraception methods avoid the potential embryofetal risks from exposure to investigational medicinal products. Highly effective methods of contraception are as follows:
- Intrauterine device
 - Intrauterine device
 - Intrauterine hormone-releasing system
 - Bilateral tubal occlusion
 - Vasectomy (partner)
 - Combined (estrogen and progestogen containing) hormonal contraception (e.g., oral, intravaginal or transdermal) associated with inhibition of ovulation. If oral contraceptives are used, they must be used in combination with a male or female condom. Female subjects should have been on the hormone contraception for at least 8 days prior to Day 1 of their parent study.
 - Progestogen-only hormonal contraception (e.g., oral, injectable, or implantable) associated with inhibition of ovulation. If oral contraceptives are used, they must be used in combination with a male or female condom. Female subjects should have been on the hormone contraception for at least 8 days prior to Day 1 of their parent study.
 - Sexual abstinence, as a form of highly effective contraception if in line with the preferred and usual lifestyle of the subject, is defined as avoiding all types of sexual activity that could result in pregnancy during the entire period of the study treatment until at least 30 days after the last dose of investigational product. The reliability of sexual abstinence needs to be evaluated in relation to the duration of the clinical study.
3. Male subjects who are sexually active with female partners of childbearing potential (defined in [Section 9.7.2.1](#)) must agree to use a condom with spermicide and to use (or have their partner use) 1 other approved method of highly effective contraception from the initiation of the study and until at least 90 days after the last dose of investigational product as listed in Inclusion Criterion #2.
4. Male patients must refrain from sperm donation from the initiation of the study and until at least 90 days after the last dose of investigational product.

5. Must provide written informed consent and agree to comply with the study protocol.

8.3. Subject Exclusion Criteria

1. Any history or presence in the last 30 days, before rolling over to this study, of other concomitant liver diseases, including any of the following:
 - Hepatitis C virus (HCV) infection with positive RNA
 - Active hepatitis B virus (HBV) infection; however, subjects who have seroconverted (hepatitis B surface antigen negative [sAg-], hepatitis B surface antibody positive [sAB+]; hepatitis B e-antigen negative [eAg-], hepatitis B e-antibody positive [eAb+]; HBV DNA negative) may be included in this study after consultation with the Medical Monitor and Sponsor Medical Monitor
 - Subjects should be excluded if positive HBV DNA or HCV RNA
 - PSC
 - Alcoholic liver disease
 - Definite autoimmune liver disease or PBC-AIH overlap
 - MASH
 - Gilbert's Syndrome (due to interpretability of bilirubin levels)
 - Rare liver conditions such as Wilson's disease, hemochromatosis, alpha-one anti-trypsin deficiency, or other conditions identified by the Principal Investigator
2. Clinical complications of PBC including:
 - Prior liver transplantation
3. Any history or presence in the last 30 days, before rolling over to this study, of any one of the following decompensating events:
 - CP Score ≥ 7
 - Clinical evidence of decompensated liver disease or evidence of portal hypertension, including but not limited to:
 - Varices (including a history of esophageal varix ligation or asymptomatic esophageal varices by endoscopy)
 - Ascites/hepatic hydrothorax
 - Spontaneous bacterial peritonitis
 - Hepatic encephalopathy
 - Jaundice (with total bilirubin >3 mg/dL [>51.3 $\mu\text{mol/L}$])
 - Biochemical evidence of hepatic impairment, decompensation, or injury including at least one of the following:
 - Total bilirubin $>\text{ULN}$

- INR >1.7
 - Albumin <3.5 g/dL
 - MELD >12
 - ALT >5x ULN
 - Known or suspected HCC
 - Prior trans-jugular intrahepatic portosystemic or peritoneovenous shunt procedure
 - Hepatorenal syndrome (type I or II) or serum creatinine >1.5 mg/dL (135 µmol/L) or estimated glomerular filtration rate (eGFR) <60 mL/min from the last lab assessment/visit in parent study, before transitioning to Study 977-311
 - Portopulmonary hypertension
 - Hepatopulmonary syndrome
4. Medical conditions that may cause non-hepatic increases in ALP (e.g., Paget's disease) or that may diminish life expectancy to <2 years, including known cancers (except carcinomas in situ or other stable, relatively benign conditions)
 5. Presence of any other disease or condition that interferes with the absorption, distribution, metabolism, or excretion of drugs including bile salt metabolism in the intestine (e.g., inflammatory bowel disease or gastric bypass procedure [gastric lap band is acceptable])
 6. Evidence or history of cholelithiasis or choledocholithiasis unless documented cholecystectomy. Gallbladder polyps if >5 mm in diameter
 7. History of chronic pancreatitis or recurrent acute pancreatitis – defined as at least 2 episodes of acute pancreatitis, with symptoms resolving between each episode
 8. History of drug-induced myopathy
 9. Chronic kidney disease (serum creatinine >1.5 mg/dL [>135 µmol/L]; CrCl <60 mL/min) or undergoing dialysis
 10. Platelet count <150,000/µL at the last visit in parent study, before transitioning to Study 977-311
 11. Known history of human immunodeficiency virus (HIV) infection
 12. History or presence of clinically concerning cardiac arrhythmias likely to affect survival during the study, QT interval of the electrocardiogram (QT) or QT interval of the electrocardiogram corrected (QTc) interval of >450 milliseconds for males and >470 milliseconds for females
 13. Severe pruritus, or required systemic treatment for pruritus (e.g., with bile acid sequestrants [BAS] or rifampicin) within 2 months of Day 1 of Study 977-311. Subjects who plan to use or will use BAS during the study will not be eligible.
 14. History of known or suspected clinically significant (CS) hypersensitivity to OCA, BZF, or other fibrates or any of their components

15. Known photoallergic or phototoxic reactions to fibrates
16. If female, known pregnancy, a positive urine pregnancy test (confirmed by a positive quantitative serum pregnancy test), or current lactation at the last visit in parent study, before transitioning to Study 977-311
17. Other CS medical conditions that are not well controlled or for which medication needs are anticipated to change during the study (e.g., Type 2 diabetes mellitus, hypothyroidism, nephritic or nephrotic syndrome, dysproteinemia, obstructive biliary disease, dyslipidemia), and/or up to the discretion of the Principal Investigator
18. Treatment with the following medications 30 days before Day 1 of Study 977-311, or plans to use these medications during the study: azathioprine, colchicine, cyclosporine, methotrexate, mycophenolate mofetil, pentoxifylline, rifampicin, statins, budesonide and other systemic corticosteroids (short-term use up to 2 weeks is permitted), monoamine oxidase inhibitors (MAOIs), and potentially hepatotoxic drugs (including α -methyl-dopa, sodium valproic acid, isoniazid, and nitrofurantoin)
19. Treatment with the following medications within 12 months before Day 1 of Study 977-311, or plans to use these medications during the study: antibodies or immunotherapy directed against interleukins or other cytokines or chemokines
20. Participation in a study of another investigational medicine or device within 30 days before Day 1 of Study 977-311 (except for Study 747-213, Study 747-214, or other eligible Sponsor study)
21. History of or ongoing alcohol or drug abuse within 1 year before Day 1 of Study 977-311. Subjects with moderate alcohol use within 3 months prior to the last visit in parent study, before transitioning to Study 977-311, will be excluded from this study. Moderate alcohol consumption is defined as 1 standard drink per day for women and 2 drinks per day for men; whereby 1 standard drink is equivalent to: 12 oz beer (5% alcohol), 5 ounces of wine (12% alcohol), or 1.5 ounces of 80 proof (40% alcohol)
22. History of noncompliance with medical regimens, or is considered by the Principal Investigator not able to meet the requirements as specified in the protocol from Day 1 throughout the duration of the study
23. Blood or plasma donation within 30 days before Day 1
24. Mental illness or other condition which may impair decision making, such that the validity of informed consent or ability to be compliant with the study is uncertain
25. A CK value on Day 1 of Study 977-311 $\geq 5 \times$ ULN or any abnormal laboratory value that is considered CS in the opinion of the Principal Investigator and Sponsor at the last visit in parent study, before transitioning to Study 977-311
26. Known or suspected nephrotic syndrome in the last 30 days, before rolling over to this study, based on the following diagnostic criteria (both Type 1 and Type 2):
 - Proteinuria, spot urine protein: albumin/creatinine ratio (ACR) of >300 mg/mmol (subjects with normal renal function and ACR values analyzed to be below the lower limits of detection are permitted)

- Serum albumin <25 g/L
- Clinical evidence of peripheral edema
- Severe hyperlipidemia (total cholesterol above >10 mmol/L)

8.4. Subject Withdrawal Criteria

Subjects who are discontinued from investigational product should be requested to continue with study visits until Month 60/EOS. Subjects who discontinue investigational product may be requested to come in for an Unscheduled Visit at the discretion of the Investigator depending on the timing of their next scheduled study visit.

8.4.1. Reasons for Mandatory Discontinuation of Investigational Product

Subjects will be monitored for potential hepatic decompensation events throughout the study. Clinical criteria for monitoring these events are summarized in [Table 5](#).

Investigational product will be discontinued permanently if the subject has evaluation, listing or completion, of a liver transplant or experiences other potential hepatic decompensation events as defined in Table 5. Subjects should be closely monitored until normalization or stabilization and should continue to return for scheduled study visits for safety follow-up.

8.4.1.1. Severe and Related Adverse Events

If a subject experiences an AE that is \geq Grade 3 in severity using criteria outlined in [Section 14.1.3](#) and is considered possibly, probably, or definitely related to the investigational product, the investigational product must be discontinued. However, subjects should be encouraged to continue study visits, despite stopping investigational product, for continued collection of safety data but may withdraw consent at any time.

8.4.1.2. Pregnancy

If a female subject becomes pregnant, she must discontinue treatment with investigational product immediately but should continue with the study visit schedule. As described in [Section 14.1.10](#), pregnancy is not considered an AE for reporting purposes.

Subjects who plan to become pregnant after study discontinuation or withdrawal should consult with their study doctor or primary HCP.

8.4.2. Other Reasons for Discontinuation of Investigational Product or Study Termination

Subjects who discontinue investigational product will be requested to continue in the study until the end of the study or at the discretion of the Sponsor; however, subjects are free to discontinue at any time.

The following events are considered appropriate reasons for a subject to be withdrawn from the study or discontinue investigational product. Subjects who discontinue investigational product are expected to continue in the study until study termination (or at the discretion of the Sponsor).

- The Investigator or Sponsor considers that it is advisable or in the best interest of the subject
- Withdrawal of consent:
 - Consent may be fully withdrawn
- Lost to follow-up
- Pregnancy
- The occurrence of clinical or laboratory AEs considered by the Investigator or Sponsor to be clinically important
- The development of any medical conditions listed in the exclusion criteria that might jeopardize patient safety ([Section 8.3](#))

The Investigator is encouraged to contact the Sponsor before discontinuing a subject from treatment. The Investigator must notify the Sponsor study monitor, also known as the Clinical Research Associate (CRA), by email as soon as possible if any subject prematurely withdraws from the study.

The Sponsor may terminate this study at any time.

8.4.2.1. Withdrawal of Consent to Continue in the Study

If the subject decides that it is in his/her best interest to discontinue from the study, he or she may withdraw consent. It is fully understood that all subjects volunteer for the study and that they may withdraw their consent to continue in the study at any time.

A reasonable effort must be made to determine the reason(s) for subject discontinuation. This information and date of contact must be recorded on the eCRF.

8.4.2.2. Lost to Follow-Up

If a subject fails to return to the clinic for a study visit, and the Investigator ceases to have contact with the subject, he or she will be withdrawn from the study. Subjects will be considered “lost to follow-up” only after reasonable, documented attempts to reach the subject prove unsuccessful.

A reasonable effort must be made to contact the subject and determine the reason(s) why a subject fails to return for a study visit or is lost to follow-up. This information and date of contact must be recorded on the eCRF.

8.4.3. Subject Discontinuation Notification

The Investigator must notify the Sponsor as soon as possible if any subject prematurely discontinues from the study. The date when the subject is withdrawn and the primary reason(s)

for discontinuation must be recorded in the eCRF; additional information may be requested by the Sponsor to complete a discontinuation narrative.

If a subject is withdrawn from the study early (regardless of the cause), all of the early termination (ET) evaluations are to be performed at the time of withdrawal, to the extent possible.

9. TREATMENT OF SUBJECTS

9.1. Investigational Product Treatment Regimen

9.1.1. Treatment Assignment

The term “investigational product” (provided as part of this clinical study) refers to the following:

- FDC tablet (OCA 5 mg + BZF 400 mg SR), once daily

Investigational product will be taken orally with water, once daily for the duration of the study. The FDC tablet must be swallowed whole and not be chewed, divided, or crushed and must be taken with food and water (ad libitum) throughout the study period. Subjects are requested to take medication in the morning. Specific instructions for dosing will be provided for PK assessment days.

9.2. Concomitant Medications

Subjects must follow the medication restrictions outlined in the inclusion and exclusion criteria ([Section 8](#)) during the study.

Relevant information about all concomitant medications (including prescribed, over the counter, or herbal preparations) taken before (i.e., within 30 days of Day 1) and during the study must be recorded in the source documents and eCRF, as well as any dose or dose regimen changes that occur during the study. Note that on days when blood is drawn for PK sample, concomitant medications should be taken after the PK sample is taken (i.e., 6 hours post dosing).

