^h AE data will be collected from the time that signed informed consent is obtained until the subject fully completes her/his participation in the study.

ⁱ CP Score will be calculated based on central laboratory evaluations and a targeted assessment of ascites and hepatic encephalopathy. Scores will be recorded on the eCRF.

^j MELD score will be calculated from serum chemistry and other parameters collected at the same visit. Scores will be recorded on the eCRF.

^l GLOBE and UK-PBC scores will be calculated from serum chemistry and other parameters and recorded on the eCRF.

^m At each study visit, the dose of investigational product should be administered daily at the same time (AM dosing is preferred to align with all study visits) starting on Day 2. All assessments must be completed before administration of investigational product and UDCA (if applicable).

ⁿ Subjects who have an onsite Day 2 visit will be administered investigational product onsite. Subjects who have a virtual Day 2 visit will self-administer investigational product during the virtual visit.

^o For subjects who have a virtual day 2 visits and have had IP shipped, the Investigator to confirm that IP was received in good condition, was untampered, and is the correct drug. Date of first IP administration should be recorded.

^p See analytes listed in [Table 11](#).

^q Urine-based β -hCG pregnancy tests must be performed in females of childbearing potential (defined in [Section 9.7.2.1](#)) prior to entry and at every visit. If positive, a confirmatory serum pregnancy (quantitative β -hCG) blood test must be performed at the central laboratory. If the confirmatory blood test is also positive, the subject may not continue in the study taking IP. (Additional testing may be conducted where required, regionally.)

^r To be performed only if test is available at qualified sites.

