13.1. PK Blood Sampling

All PK blood collections must be performed at the clinical site and not at a local lab.

Subjects need to be in fasting condition for at least 8 hours prior to collection of PK samples. A [REDACTED] through Month 60 (EOS), and the ET and/or Unscheduled Visits (if applicable). A [REDACTED] also must be collected within 7 days of a safety event (e.g., event related to potential hepatic or muscular injury).

The acceptable windows for sample collection on Month 1 through Month 60 Visits are shown in Table 7. There is no window required for the Day 1 Visit as investigational product will not be administered.

Table 7: Acceptable Windows for Pharmacokinetic Sample Collection (Month 1 through Month 60)

Nominal Sampling Time	Acceptable Sampling Window
[REDACTED]	30 minutes ±15 minutes before dosing

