11.2 Disease-Specific Symptoms as Assessed by Questionnaires			Removed to align with other FDC Phase 3 study and to reduce subject burden.
13.1 PK Blood Sampling	
Subjects need to be in fasting condition for at least 8 hours prior to collection of PK samples. A [REDACTED]
 
[REDACTED]
 
[REDACTED] through Month 60 (EOS/ET).
	
Subjects need to be in fasting condition for at least 8 hours prior to collection of PK samples. [REDACTED]
 
[REDACTED]
 
[REDACTED] through Month 60 (EOS), and the ET and/or Unscheduled Visits (if applicable). [REDACTED]
	
Updates made to align with changes to visit schedule.
 
Language indicating that the investigational

Section	Original Text (Version 1.0, 25 Jan 2024)	Revised Text (Version 2.0, 18 Nov 2024)	Key Change Reasons/ Justification for Change								
	
Subjects should take investigational product with the provided low-fat meal or meal replacement drink.
 
The acceptable windows for sample collection are shown in Table 7.
 
Table 7: Acceptable Windows for Pharmacokinetic Sample Collection
 

Nominal Sampling Time	Acceptable Sampling Window	

	30 minutes before dosing	

	Nominal Sampling Time	Acceptable Sampling Window	

	30 minutes before dosing	
sample also must be collected within 7 days of a safety event (e.g., event related to potential hepatic or muscular injury).
 
The acceptable windows for sample collection on Month 1 through Month 60 Visits are shown in Table 7. There is no window required for the Day 1 Visit as investigational product will not be administered.
 
Table 7: Acceptable Windows for Pharmacokinetic Sample Collection (Month 1 through Month 60)
 

Nominal Sampling Time	Acceptable Sampling Window	

	30 minutes ±15 minutes before dosing	

	Nominal Sampling Time	Acceptable Sampling Window	

	30 minutes ±15 minutes before dosing	
product to be taken with a low fat meal or meal replacement drink is only relevant for post-dose PK sampling, which is not included in this study. Therefore, the language was removed.
 
PK samples were added for unscheduled visits if applicable to inform exposure safety analyses.

Nominal Sampling Time	Acceptable Sampling Window										

	30 minutes before dosing										
Nominal Sampling Time	Acceptable Sampling Window										

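### Protocol Section 9.2 equates the PK sample with 6 hours after dosing, while Table 7 sets it 15 to 45 minutes before dosing; the two must be reconciled.

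*Protocol*

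**What the plan says.** Four places in the current protocol bear on when the PK sample is drawn.

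- **Section 9.2, Concomitant Medications.** On days with a PK draw, "concomitant medications should be taken after the PK sample is taken (i.e., 6 hours post dosing". The parenthesis defines the sample time as 6 hours after the dose and ties the other medicines to it.
- **Section 13.1 and Table 7.** "The acceptable windows for sample collection on Month 1 through Month 60 Visits are shown in Table 7", and the one visible window is "30 minutes ±15 minutes before dosing". For Day 1, "There is no window required for the Day 1 Visit as investigational product will not be administered". For safety events, a sample "also must be collected within 7 days of a safety event", with no clock time relative to dose in the visible text.
- **Section 7.1.3, Table 3, footnote m.** "All assessments must be completed before administration of investigational product and UDCA (if applicable".
- **Appendix B, reason given for the Version 2.0 change to Section 13.1.** Meal wording was taken out because it "is only relevant for post-dose PK sampling, which is not included in this study".

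On analysis, Protocol Section 15.6 plans descriptive summaries by scheduled post-baseline visit. SAP Section 5.5 defines no analysis windows and includes only scheduled visits.

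**The concern.** A site reading Section 9.2 and a site reading Table 7 would do different things on the same study day. If the first site draws at 6 hours, its result measures a different part of the dosing interval from a pre-dose result, yet both carry the same visit label. If a site draws before the dose but also obeys the 6-hour wording, it delays the subject's other medicines well past a sample that is already in the tube. Sections 9.2.3 and 9.2.4 allow anticoagulants and antidiabetics with extra monitoring, so some of the delayed medicines may be ones whose timing matters. At stake are the interpretability of the PK summaries and consistent conduct at sites.

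**Working it through.** The plan gives no figure to reproduce. The check is a side-by-side reading plus clock arithmetic.

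**1. Times relative to dose (dose = 0).**

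| Source | Sample time |
|---|---|
| Section 9.2 | +6 h |
| Table 7, nominal | −0.5 h |
| Table 7, limits (−30 ± 15 min) | −0.75 h to −0.25 h |
| Table 3, footnote m | before 0 |

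**2. Gap between the two instructions.**

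- Shortest: 6 − (−0.25) = 6.25 h
- Nominal: 6 − (−0.5) = 6.5 h
- Longest: 6 − (−0.75) = 6.75 h

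A site that samples within Table 7 and then waits for the Section 9.2 time holds other medicines for 6 h 15 min to 6 h 45 min after the draw.

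**3. Could the 6-hour time belong to some other sample?** Day 1 has no dose. The safety-event sample has only a 7-day limit. No visible text schedules a draw 6 hours after dosing, and the Appendix B reason says that post-dose sampling is "only relevant for post-dose PK sampling, which is not included in this study" wording, that is, outside this study. That column explains a deletion elsewhere, so it is corroboration only; Section 9.2 and Table 7 conflict without it.

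**4. Does redaction explain it?** The nominal-time label in Table 7 and part of the Section 13.1 sampling sentence are blacked out. The window itself is legible and states that it precedes dosing. Footnote m is fully legible and agrees with it.

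**5. Number of visits.** Table 3 gives Months 1, 3, 6 and 12 (4 visits), then every 6 months from Month 18 to Month 60 (8 visits): 4 + 8 = 12. This is an upper limit. The PK row of Table 3 is not visible, so a draw at each visit is an assumption. Table 3 and Section 9.7.2.4 give no investigational product at Month 60, so at most 12 − 1 = 11 of these visits have an on-site dose from which either time can be counted.

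**6. Would the analysis separate the two kinds of sample?** The PK Population (Protocol Section 15.1, SAP Section 4.2) excludes major deviations that could affect plasma exposure, but it does not name the Table 7 window. A draw that follows Section 9.2 to the letter might not be classed as a major deviation. No visible rule makes the summaries use actual time since dose.

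**The case against.** The strongest reply is that Section 9.2 contains a stray parenthesis in a note about other medicines, while sampling is governed by a dedicated section with its own window table. Section 9.1.1 promises specific dosing instructions for PK days, and Section 14.2.6 refers to separate procedural manuals; neither is available here, and either may already steer sites to one time. A 6-hour draw would also fall outside Table 7 and might be excluded from the PK Population. PK reporting in the study report is descriptive, the primary objective is safety and tolerability, and no hypothesis is tested.

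Much of this stands. It makes widespread mixed sampling less likely and limits the consequence. It does not remove two incompatible statements from the protocol, and exclusion as a major deviation is possible rather than assured.

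A reader might also infer more than the documents support:

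- **A very large difference in concentration.** Taking a pre-dose draw as 23.5 h after the previous dose, the gap to 6 h is 23.5 − 6 = 17.5 h. With the 2.4-hour half-life in Section 5.5.2.2, that is 17.5 / 2.4 = 7.29 half-lives, or about 157-fold. But that half-life belongs to the 200 mg immediate-release tablet, and Section 10.1 describes sustained-release bezafibrate. The sum also assumes simple exponential decline and ignores OCA, for which Section 5.4.1 describes multiple peaks and prolonged exposure. The figure should not be used.
- **A prolonged fast.** Subjects arrive fasted, but Section 9.1.1 has the tablet taken with food, so the hours after the dose are not a fasted interval.
- **A delay with no purpose.** That presumes the pre-dose time is the intended one. Most of the text points that way, but the sponsor must confirm it.

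**Conclusion.** The contradiction is real, lies in current text, and is not a product of redaction. Its supportable size is the 6.25 to 6.75 hour gap at each affected visit. Two consequences are possible: unlike samples summarised under one visit, or other medicines delayed for hours after the draw. Neither is shown to occur; each follows if a site takes Section 9.2 literally and the separate PK-day instructions do not correct it. The up-to-12-visit count rests on PK being drawn at every scheduled visit from Month 1. This is an internal inconsistency that should be corrected, and no primary conclusion turns on it.

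**What to change.** The sponsor should reconcile Section 9.2, Section 13.1 with Table 7, and Table 3 footnote m, so that the protocol states one PK sampling time and the concomitant-medication sentence refers to that time. The reconciled text should also say what the time is counted from at Month 60, where no investigational product is given. Which time applies, and when other medicines are taken, is for the sponsor to settle; no dosing or medication-timing rule is proposed here.

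In the SAP, state that PK concentrations are summarised by actual time relative to dose, and that samples outside the reconciled window are listed separately and not pooled with the visit summary.

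The cost is a small protocol wording change or site memo, a check that the PK-day instructions and manuals agree, and a programming step. That step assumes that actual draw and dose times are recorded, which the visible text does not confirm and which should be checked.
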